# 11.4. General Considerations for Data Analysis

Data will be listed and summarized according to GSK reporting standards, where applicable. Complete details will be documented in the Reporting and Analysis Plan (RAP).

#### 11.4.1. Withdrawal

Patients that drop out will be replaced until 20 subjects have been determined to be evaluable.

## 11.4.2. Missing Data

Missing data will not be imputed.

#### 11.4.3. Assessment Windows

Safety assessments that occur prior to the administration of the first administration of lapatinib will be considered screening assessments. Safety assessments that occur after dosing has begun will be considered as having occurred while on treatment. Pharmacokinetic measurements will be associated with the treatment day on which the assessment occurred. Pharmacodynamic measures will be associated with the day on which the measure was taken.

#### 11.4.4. Other issues

Since multiple sites will be involved in the conduct of this study, an exploratory analysis may be undertaken to determine if there appear to be gross site effects associated with the primary endpoints.

# 11.5. Safety Analyses

Safety assessments conducted at screening and at various times throughout the study include blood pressure, heart rate, hematology and clinical chemistry. Adverse events will be monitored throughout the study.

## 11.5.1. Extent of Exposure

Extent of exposure to lapatinib will depend on the patient's tolerability to the dose administered and the date post-exposure biopsy or resection.

#### 11.5.2. Adverse Events

The investigator is responsible for the detection and documentation of events meeting the definition of an AE or SAE as provided in this protocol. Whenever there is a safety evaluation, the investigator or study site personnel will be responsible for detecting AEs and SAEs, as detailed in Section 10 of the protocol. In order to fulfill international safety reporting obligations, the investigator should include in his or her assessment any SAEs resulting from study participation (e.g., complications resulting from the taking of a blood sample).

Adverse Events will be coded and grouped using the Medical Dictionary for Regulatory Activities (MedDRA). All AEs will be listed. If warranted, by the number of AEs, a summary by treatment group of the number and percent of patients reporting each event at least once will be produced.

#### 11.5.3. Clinical Laboratory Evaluations

Hematology and clinical chemistry values will be listed for each patient and flagged high or low relative to the normal range, where applicable. Median and range pre- and post-dose values will be plotted by treatment group. Pre-dose values will be used to assess laboratory shifts occurring post-dose. A comparison of pre-study and post-study follow-up values will be performed to identify any parameters that have not returned to pre-study levels.

#### 11.5.4. Other Safety Measures

Vital signs will be listed for each subject. Median profiles will be plotted by treatment group.

# 11.6. Clinical Pharmacology Data Analyses

# 11.6.1. Pharmacokinetic Analyses

Lapatinib plasma and intratumoral concentration data will be summarized and displayed in both tabular and graphical form.

# 11.6.2. Pharmacodynamic Analyses

Each patient will be measured for biomarker activity level in tumor obtained pre- and post-dose. For each marker, a one-way analysis of covariance of the post-dose measurement will be performed with a biological marker of cellular proliferation, cellular apoptosis, or other biological marker deemed relevant to pathways regulating cancer

pathophysiology as a classification variable and the pre-dose level of the marker as a covariate. Transformation, e.g., logarithms, of pre- and post-dose marker levels may be necessary to satisfy analysis assumptions.

All pharmacodynamic endpoints of interest from all study sessions will be descriptively and/or graphically summarized, as appropriate to the data.

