# 3. ENDPOINT(S)

### 3.1. Primary

• Comparison of the effects of lapatinib on biomarkers involved in regulating tumor cell proliferation and survival (e.g., ErbB2, ERK1/2, AKT, and other downstream pathways regulated by ErbB receptor signaling) in pre-treatment and post-treatment breast tumor tissue samples.

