### 4. STUDY DESIGN

This will be a single arm, open-label phase I study. Patients will receive 1500mg of lapatinib administered daily for a minimum of 9 days and continue treatment until surgical resection (≤24 hours).

Prior to entering the study, the documented ErbB2 status will be required for each patient. Only patients with treatment-naïve, ErbB2 positive, as defined by either overexpression of ErbB2 (3+) by semi-quantitative IHC or amplification of the ErbB2 gene by fluorescence in situ hybridization (FISH), breast tumors measuring 1 cm or greater will be eligible for the study. For eligible patients, archived tumor tissue obtained at diagnosis will represent the pre-treatment biopsy and be required for entry into the study. The pre-treatment biopsy tissue will be examined using technologies for measuring biomarkers involved in regulating tumor cell proliferation and survival (e.g., ErbB2, ERK1/2, AKT, and other downstream pathways regulated by ErbB receptor signaling). Patients will receive treatment with lapatinib for a minimum of 9 days and continue treatment until 24 hours prior to surgical resection. Patients will have their post-treatment surgical resection performed within 24 hours of last lapatinib dose. Tumor tissue obtained at resection will be examined for biomarkers as described above and compared with the results from the pre-treatment biopsy. In addition, tumor obtained at the time of resection will be examined for steady state, trough concentrations of lapatinib.

Detailed instructions on processing and shipping archived and resected tissue are included in the SRM.

Safety (AEs, clinical laboratory values) will be assessed throughout the study.

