#### 11. DATA ANALYSIS AND STATISTICAL CONSIDERATIONS

# 11.1. Hypotheses

No formal hypotheses are being tested. The study will focus on obtaining point estimates and 90% confidence intervals of biomarker differences derived from the pre-to-post tumor tissue.

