# 11.2. Sample Size Considerations

Twenty evaluable subjects are needed for biomarker analyses.

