# 11.2.1. Sample Size Assumptions

In preliminary analysis of the tumor biomarkers in the phase I clinical study EGF10004, the standard deviation of the pre-dose to post-dose percent change in individual biomarkers ranged from 17% to over 600% across multiple dose levels of lapatinib. Although the variability of tumor biomarkers measured in a more homgenous population (i.e. all breast cancer) may be reduced, it is not practical to frame this study as confirmatory hypothesis testing. Thus, results from this study should be viewed as exploratory data analysis, and proposed sample sizes are based on logistic feasibility.

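### The only inferential model in Section 11.6.2 does not, as specified, produce the pre-to-post biomarker differences and 90% confidence intervals that Section 11.1 makes the focus of this single-arm study

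*Supplement*

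**What the plan says.** - **Design.** Section 4: "This will be a single arm, open-label phase I study". There is no comparator.
- **Primary endpoint.** Section 3.1: "Comparison of the effects of lapatinib on biomarkers involved in regulating tumor cell proliferation and survival", assessed "in pre-treatment and post-treatment breast tumor tissue samples".
- **Estimation target.** Section 11.1 disclaims formal hypotheses and then states: "The study will focus on obtaining point estimates and 90% confidence intervals of biomarker differences derived from the pre-to-post tumor tissue".
- **Sample size.** Section 11.2: "Twenty evaluable subjects are needed for biomarker analyses". Section 11.2.1 adds that "proposed sample sizes are based on logistic feasibility", and that in an earlier phase I study the standard deviation of the percent change in individual biomarkers "ranged from 17% to over 600% across multiple dose levels of lapatinib".
- **Model.** Section 11.6.2: "For each marker, a one-way analysis of covariance of the post-dose measurement will be performed with a biological marker of cellular proliferation". The sentence goes on to allow an apoptosis marker or another relevant biological marker instead. Whichever is used enters as the classification variable, and the pre-dose level of the analysed marker is the covariate. A transformation such as logarithms is allowed for. The section closes with a general promise of descriptive or graphical summaries. It names no change score, paired analysis, adjusted mean or confidence interval.
- **Deferred detail.** Section 11.4 leaves complete details to a Reporting and Analysis Plan, which is not among the documents.
- **Origin.** The Amendment 03 summary of changes (Appendix 8) shows that the three-arm version used the same model form with treatment group as the factor, followed by a sentence on adjusted least squares means per regimen. Amendment 03 put the biological marker in place of treatment group and removed that sentence. This is cited for origin only; the mismatch is in the current text.

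**The concern.** With one arm, the drug effect is measured by how far each patient's marker moves from the pre-treatment to the post-treatment sample. Section 11.6.2 should therefore lead to an estimate of that movement. Its model instead takes the post-dose level as response, adjusts for the pre-dose level, and compares patients classified by a different marker. That asks whether patients in one marker class end at a different level from patients in another class who started at the same level. It does not ask how far the marker moved.

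The factor raises a second matter. The text does not say whether the classifying marker is read before or after treatment. If it were read after treatment, patients would be grouped by something the drug may have changed, and a subgroup contrast could then arise from the grouping.

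At stake is the primary result. An analyst who reports the output of the 11.6.2 model as the biomarker analysis would report a subgroup contrast where the reader of Section 11.1 expects a pre-to-post effect with its interval.

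**Working it through.** **Figures in the plan.** The current version has no power or precision calculation to reproduce; 20 rests on feasibility. The confidence-interval half-widths of 36, 55 and 18 points in the Amendment 01 summary of changes belong to a superseded contrast between two schedules and do not carry over.

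**Step 1: what the model estimates.** Write the model for one marker as

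post = a + g × class + b × (pre − mean pre) + error.

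The factor effect g is the difference in post-dose level between classes at equal pre-dose level. If the drug lowers every patient's marker by the same amount on the log scale, the shift goes into a, and g is unchanged.

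**Step 2: simulation of that statement.** Assumptions, none from the documents: log scale; 20 patients; two classes of 10, unrelated to the marker; pre-dose SD 1; slope b of 0, 0.5 or 1 with error variance 1, 0.75 or 0.25; 2,000 runs per setting.

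| True change | Mean of g over the three slopes | 90% CI for g excludes 0 | Paired mean log change | Coverage of paired 90% CI |
|---|---|---|---|---|
| 0% (log 0) | -0.016 to 0.009 | 8.0% to 10.3% | 0.000 to 0.009 | 0.889 to 0.914 |
| -50% (log -0.693) | -0.011 to 0.008 | 9.7% to 11.1% | -0.700 to -0.692 | 0.883 to 0.900 |
| -75% (log -1.386) | 0.002 to 0.007 | 9.6% to 11.1% | -1.390 to -1.379 | 0.889 to 0.901 |

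The exclusion rate for g stays near the 10% expected by chance in every row. The planned contrast does not distinguish an inactive drug from one that cuts the marker by three quarters.

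**Step 3: could the same model give the change by an extra contrast?** Yes, as a point estimate: take the adjusted post-dose mean at the average pre-dose level and subtract the pre-dose mean. In the simulation this equalled the paired mean change. Its standard interval, however, treats the pre-dose values as fixed:

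- variance used by the standard interval: (error variance)/20;
- variance of the mean change across patients: [error variance + (1 − b)² × pre-dose variance]/20.

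The interval is therefore too narrow by the square root of the ratio. With t(0.95, 17) = 1.740:

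| Slope b | Variance ratio | Width factor | Effective multiplier | Approximate coverage | Simulated coverage |
|---|---|---|---|---|---|
| 0 | 1/(1 + 1) = 0.50 | 0.707 | 1.230 | 0.76 | 0.762 to 0.777 |
| 0.5 | 0.75/(0.75 + 0.25) = 0.75 | 0.866 | 1.507 | 0.85 | 0.836 to 0.856 |
| 1 | 0.25/(0.25 + 0) = 1 | 1 | 1.740 | 0.90 | 0.884 to 0.900 |

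The nominal 90% is reached only when the slope is 1.

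**Step 4: precision of the direct analysis.** One-sample half-width = t(0.95, 19) × SD/√20 = 1.729 × SD/4.472 = 0.387 × SD.

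- SD 17% (low end in Section 11.2.1): 0.387 × 17 = ±6.6 percentage points.
- SD 600% (the upper figure there is over 600%, so this is a floor): 0.387 × 600 = ±232 percentage points.

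Precision will differ greatly between markers, which is a reason to report the interval that Section 11.1 promises for each.

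**The case against.** The strongest reply is that the two sections can be read together: Section 11.1 commits the study to the change and its interval, and Section 11.6.2 adds an association analysis. The closing sentence of 11.6.2 on descriptive summaries can include mean changes, and the unseen Reporting and Analysis Plan may supply the estimator. The study is exploratory, and Sections 5.1 and 11.3 require both samples, so the change remains computable.

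Much of this stands, and it rules out several stronger readings that a reader might infer:

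- *That the model cannot yield the change, or that the primary objective must go unestimated.* Step 3 shows that an added contrast recovers the point estimate, and Section 11.1 still commits to the estimate and interval.
- *That the factor is a continuous marker to be cut into classes, or is a post-dose value.* The text says neither. The ErbB2 tests in Section 5.2.1 are reported in categories, so a naturally categorical marker is possible. Conditioning on a post-treatment value is a conditional risk only.
- *That the planned contrast is wholly left over from three arms.* The model form was kept, but Amendment 03 deliberately rewrote the factor.
- *That a subgroup interval about twice as wide measures the harm.* It would compare different quantities, under assumed class sizes and equal standard deviations.

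Choice of classes and similar detail may properly be left to the analysis plan. What does not fall away is that the protocol names one model and that model targets a different quantity from the one in Section 11.1. The descriptive sentence promises no interval, and an analysis plan written to follow 11.6.2 would carry the mismatch forward. Being exploratory does not help, since estimation is the stated focus.

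**Conclusion.** The concern holds in this form: as specified, the only inferential model in Section 11.6.2 does not produce the pre-to-post differences and 90% intervals of Section 11.1. This follows from the model's structure and needs no assumed numbers.

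The size of the mismatch is illustrated by simulation. The planned contrast averaged between -0.02 and 0.01 log units across true changes of 0%, -50% and -75%, provided the classifying marker is unrelated to the analysed one. Improvising the change from this model could give intervals with coverage of about 76% to 86% in place of 90%, under assumed slopes of 0 to 0.5; with a slope of 1 there is no loss. The documents give no slope, so the actual shortfall is unknown.

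No data are lost. The fault lies in the specification and can be mended before analysis.

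**What to change.** Amend Section 11.6.2, and carry the same text into the Reporting and Analysis Plan:

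1. For each marker, make the main analysis the within-patient pre-to-post change with a one-sample (paired) t 90% confidence interval. One suitable form is log(post/pre), back-transformed to a geometric mean ratio. Where a marker can read zero, name in advance an untransformed or other suitable scale.
2. Keep the model relating each marker to a proliferation, apoptosis or other marker, but label it secondary and exploratory, and state that the pre-dose value of the classifying marker is used.

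The cost is wording in the protocol and analysis plan. It needs no new patients, samples or assays, because paired tissue is already required of every evaluable patient.

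### Sections 11.1 and 11.6.2 do not match: the target is the pre-to-post biomarker difference with a 90% interval, but the named terms of the only model do not estimate it

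*Supplement*

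**What the plan says.** The primary endpoint in Section 3.1 is "Comparison of the effects of lapatinib on biomarkers involved in regulating tumor cell proliferation and survival", assessed in tumour tissue taken before and after treatment. Section 11.1 says "No formal hypotheses are being tested" and then gives the aim: "The study will focus on obtaining point estimates and 90% confidence intervals of biomarker differences derived from the pre-to-post tumor tissue".

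Section 4 fixes the design: "This will be a single arm, open-label phase I study". Section 7.4 gives every patient the same regimen.

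Section 11.6.2 names one model. It begins "For each marker, a one-way analysis of covariance of the post-dose measurement will be performed with a biological marker of cellular proliferation", allows a marker of apoptosis or another relevant marker in that place, and ends "pathophysiology as a classification variable and the pre-dose level of the marker as a covariate". Log transformation is allowed if the model assumptions need it. The section's only other output is that "All pharmacodynamic endpoints of interest from all study sessions will be descriptively and/or graphically summarized". Section 11.4 leaves full details to the RAP, which is not among the documents.

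**The concern.** The target in Section 11.1 is a within-patient quantity: how far each marker moves between the diagnostic sample and the resected tumour. The model in Section 11.6.2 takes the post-dose level as its response and compares groups of tumours defined by some other marker. Its class term asks whether tumours of one class end at a different level from tumours of another class, given the same starting level. That is a reasonable exploratory question, but it is not the one in Sections 3.1 and 11.1.

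At stake is whether the section that specifies the primary analysis leads the analyst to the primary estimate. A RAP that only elaborates Section 11.6.2 would specify class comparisons in detail and could leave the paired estimate and its interval undefined.

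**Working it through.** **Plan's own figure.** There is none to reproduce. Section 11.2 asks for 20 evaluable patients, and Section 11.2.1 bases this on feasibility, with no effect size, power or target precision.

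**Step 1: structure of the model.** Write the ANCOVA as post = a + c(class) + b × pre + e. Add a constant d to every post-dose value, which is what a uniform change does on the model scale. The design matrix contains an intercept, so least squares moves a to a + d and leaves c, b, the residuals and all standard errors of c and b as they were. The class test is therefore unaffected by d, whatever the sample size, class sizes, SD or pre/post correlation.

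**Step 2: can the change be recovered?** Yes, with a contrast the protocol does not name. Take the adjusted post-dose mean at the mean pre-dose level, averaged over the sample's class mix, and subtract the mean pre-dose level. This equals the raw mean change (largest discrepancy about 2e-15). Its model-based 90% interval treats the pre-dose values as fixed. In simulation (n = 20, two classes of 10, pre/post correlation 0.5, 10,000 runs per shift) it covered the true mean change in only about 84–85% of runs.

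**Step 3: class term against paired interval, standardised scale.** Same simulation, no class difference, two-sided 10% level to match a 90% interval.

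| Common shift (SD) | Class term flagged | Paired 90% interval excludes 0 |
|---|---|---|
| 0 | 9.5% | 10.0% |
| −0.5 | 10.2% | 69.6% |
| −1 | 10.3% | 99.7% |
| −2 | 10.1% | 100% |

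**Step 4: log-ratio scale, with a range of SDs.** The documents give no SD for log(post/pre), so 0.4, 0.8 and 1.2 are assumptions. The paired 90% interval is mean ± t(0.95, 19) × SD/√20, with t = 1.729. The chance that it excludes zero comes from the noncentral t distribution on 19 degrees of freedom, with noncentrality ln(ratio)/(SD/√20). For a 50% fall at SD 0.8 this is −0.693/0.179 = −3.87.

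| SD of log ratio | 50% fall: noncentrality | Excludes no change | 25% fall: noncentrality | Excludes no change |
|---|---|---|---|---|
| 0.4 | −7.75 | about 100% | −3.22 | 93% |
| 0.8 | −3.87 | 98% | −1.61 | 46% |
| 1.2 | −2.58 | 80% | −1.07 | 27% |

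Simulated under the same settings (two classes of 10, pre-dose log SD 1 assumed), the class term was flagged in about 10% of trials in every cell, and equally often with no change at all.

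**Step 5: precision of the mended analysis on the protocol's own scale.** Section 11.2.1 quotes SDs of percent change from 17% to over 600%. With n = 20 the half-width is 1.729 × 17/√20 = 6.6 percentage points at the low end and 1.729 × 600/√20 = 232 points at 600%.

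**The case against.** The strongest reply is that the target estimate is already in the plan. Section 11.1 belongs to the same statistical section, nothing in 11.6.2 cancels it, and 11.6.2 does not call the ANCOVA the primary or only analysis. Descriptive summaries of all pharmacodynamic endpoints are promised, and the mechanics of a paired interval are commonly left to a RAP. All of this stands. A reader might infer that the trial will fail to report its primary result, or that the model cannot show any change. The documents support neither: the promise in 11.1 remains, and the fitted intercept holds the shift.

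A reader might also infer that a class p-value will be taken as evidence for or against a drug effect. No passage plans a test of the class term or gives it that meaning, and Section 11.2.1 calls the work exploratory. The 10% level used above is a yardstick, not a planned test.

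Finally, the flat class term follows by algebra, so the simulations illustrate it and do not add evidence. The paired percentages depend heavily on the assumed SD, which is why a range is shown.

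What the reply does not remove is that the protocol did not leave the method open. It names a specific model whose named terms differ from its stated target. A commitment to descriptive or graphical summaries does not commit to the 90% interval in 11.1. Exploratory status removes hypothesis tests, not the quantity to be estimated.

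**Conclusion.** The mismatch between Sections 11.1 and 11.6.2 is real. The class contrasts and baseline slope do not estimate the pre-to-post difference, and no output is requested from the intercept, where a common change goes. This rests on the algebra alone and needs no assumption about variability.

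The illustration of size does rest on assumptions: 20 patients, two equal classes, a uniform change, and a log-ratio SD of 0.4 to 1.2. Over that range a paired interval excludes no change in about 80–100% of trials for a 50% fall and 27–93% for a 25% fall, against about 10% for the class term.

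The finding goes no further than a gap between target and named model. It does not show that the change will go unreported. Nor would the paired estimate isolate an effect of lapatinib: in one uncontrolled arm it measures change from archived diagnostic tissue to resected tissue.

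**What to change.** In Section 11.6.2, name as the main analysis for each marker the mean within-patient post-minus-pre change with a 90% t interval, in the pharmacodynamic population of Section 11.3. Where the data support it, work on the log scale and back-transform to a geometric mean percent change; this fits the section's existing allowance for transformation.

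Keep the class ANCOVA as a labelled exploratory comparison between tumour classes, and state that it does not estimate the pre-to-post change. Describe the paired result as change from archived diagnostic to resected tissue, not as an isolated drug effect.

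The cost is one paragraph in Section 11.6.2 and matching text in the RAP. The paired samples are already required, so no new data or patients are needed.
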